9. DEFINITION OF THE PRIMARY AND SECONDARY VARIABLES

9.1. Primary Variables

Stroop Color-Word Test

The Stroop Color-Word Test is based on the observation that individuals can read words much faster than they can identify and name colors. The cognitive dimension tapped by the Stroop is associated with cognitive flexibility, resistance to interference from outside stimuli, creativity, and psychopathology – all of which influence the individual's ability to cope with cognitive stress and process complex input. Whether the test is used as a screener or as part of a general battery, its quick and easy administration, validity, and reliability make it an especially attractive instrument. Furthermore, it is not culturally biased (Cohen, 2002). Thus, this unique test is an ideal way to screen for neuropsychological deficits.

MoCA

Montreal Cognitive Assessment (MoCA) was designed as a rapid screening instrument for mild cognitive dysfunction. It assesses different cognitive domains: attention and concentration, executive functions, memory, language, visuoconstructional skills, conceptual thinking, calculations, and orientation. Time to administer the MoCA is approximately 10 minutes. The total possible score is 30 points; a score of 26 or above is considered normal.

Processing Speed Index, Wechsler Adult Intelligence Scale, Third Edition

The Processing Speed Index (PSI) assesses skills such as focusing attention and quick scanning as well as discriminating between and sequentially ordering visual information. It requires persistence and planning ability, but it is sensitive to motivation, difficulty working under time pressure, and motor coordination as well. It is also related to reading, mathematical, and memory

skills. Cultural factors seem to have little impact on processing speed. Processing Speed (PS) refers to the speed at which cognitive processes can be performed.

Digit Span, Wechsler Adult Intelligence Scale, Third Edition

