| HDRS_v1-baseline | Hamilton Depression Rating Scale Baseline Difference Day 100 |
| HDRS_v2-baseline | Hamilton Depression Rating Scale Baseline Difference Day 180 |
| HDTS_1 | Hamilton Depression Rating Scale - Total score at Visit 1 - Baseline |
| HDTS_2 | Hamilton Depression Rating Scale - Total score at Visit 2 – Day 100 |
| HDTS_3 | Hamilton Depression Rating Scale - Total score at Visit 3 – Day 180 |
| MOCA_v1-baseline | Montreal Cognitive Assessment Baseline Difference Day 100 |
| MOCA_v2-baseline | Montreal Cognitive Assessment Baseline Difference Day 180 |
| MOTS_1 | Montreal Cognitive Assessment – Total Score at Visit 1 - Baseline |
| MOTS_2 | Montreal Cognitive Assessment – Total Score at Visit 2 – Day 100 |
| MOTS_3 | Montreal Cognitive Assessment – Total Score at Visit 3 – Day 180 |
| MTT1_v1-baseline | CANTAB Multitasking Test – Total Correct Baseline Difference Day 100 |
| MTT1_v2-baseline | CANTAB Multitasking Test – Total Correct Baseline Difference Day 180 |
| MTT2_v1-baseline | CANTAB Multitasking Test – Total Incorrect Baseline Difference Day 100 |
| MTT2_v2-baseline | CANTAB Multitasking Test – Total Incorrect Baseline Difference Day 180 |
| MTTTC01_1 | CANTAB Multitasking Test – Total Correct at Visit 1 - Baseline |
| MTTTC01_2 | CANTAB Multitasking Test – Total Correct at Visit 2 – Day 100 |
| MTTTC01_3 | CANTAB Multitasking Test – Total Correct at Visit 3 – Day 180 |

Cerebrolysin and repetitive Transcranial Magnetic Stimulation (rTMS) in patients with Traumatic Brain Injury

Version 1.0

| MTTTC02_1 | CANTAB Multitasking Test – Total Incorrect at Visit 1 - Baseline |
|---------------------|--|
| MTTTC02_2 | CANTAB Multitasking Test – Total Incorrect at Visit 2 – Day 100 |
| MTTTC02_3 | CANTAB Multitasking Test – Total Inorrect at Visit 3 – Day 180 |
| OTS01_1 | CANTAB One Touch Stockings of Cambridge-Problems solved on first choice at Visit 1 - Baseline |
| OTS01_2 | CANTAB One Touch Stockings of Cambridge-Problems solved on first choice at Visit 2 – Day 100 |
| OTS01_3 | CANTAB One Touch Stockings of Cambridge-Problems solved on first choice at Visit 3 – Day 180 |
| OTS02_1 | CANTAB One Touch Stokings of Cambridge-Mean choices to correct at Visit 1 - Baseline |
| OTS02_2 | CANTAB One Touch Stokings of Cambridge-Mean choices to correct at Visit 2 – Day 100 |
| OTS02_3 | CANTAB One Touch Stokings of Cambridge-Mean choices to correct at Visit 3 – Day 180 |

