| OTS1_v1-baseline | CANTAB One Touch Stockings of Cambridge-Problems solved on first choice Baseline Difference Day 100 |
| OTS1_v2-baseline | CANTAB One Touch Stockings of Cambridge-Problems solved on first choice Baseline Difference Day 180 |
| OTS2_v1-baseline | CANTAB One Touch Stokings of Cambridge-Mean choices to correct Baseline Difference Day 100 |
| OTS2_v2-baseline | CANTAB One Touch Stokings of Cambridge-Mean choices to correct Baseline Difference Day 180 |
| PRESDT | Presentation Date |
| PSCNUM_1 | Processing Speed Index – Digit Symbol Coding Number Correct at Visit 1- Baseline |
| PSCNUM_2 | Processing Speed Index – Digit Symbol Coding Number Correct at Visit 2 – Day 100 |
| PSCNUM_3 | Processing Speed Index – Digit Symbol Coding Number Correct at Visit 3 – Day 180 |
| PSI_DSC_v1-baseline | Processing Speed Index – Digit Symbol Coding Number Correct Baseline Difference Day 100 |
| PSI_DSC_v2-baseline | Processing Speed Index – Digit Symbol Coding Number Correct Baseline Difference Day 180 |
| PSI_SS_v1-baseline | Processing Speed Index – Symbol Search Number Correct Baseline Difference Day 100 |
| PSI_SS_v2-baseline | Processing Speed Index – Symbol Search Number Correct Baseline Difference Day 180 |
| PSSCNUM_1 | Processing Speed Index – Symbol Search Number Correct at Visit 1 - Baseline |
| PSSCNUM_2 | Processing Speed Index – Symbol Search Number Correct at Visit 2 – Day 100 |
| PSSCNUM_3 | Processing Speed Index – Symbol Search Number Correct at Visit 3 – Day 180 |
| PSSINUM_1 | Processing Speed Index – Symbol Search Number Incorrect at Visit 1 - Baseline |
| PSSINUM_2 | Processing Speed Index – Symbol Search Number Incorrect at Visit 2 – Day 100 |
| PSSINUM_3 | Processing Speed Index – Symbol Search Number Incorrect at Visit 3 – Day 180 |
| RTI1_v1-baseline | CANTAB RTI - Five choice movement time - Raw score Baseline Difference Day 100 |
| RTI1_v2-baseline | CANTAB RTI - Five choice movement time - Raw score Baseline Difference Day 180 |
| RTI2_v1-baseline | CANTAB RTI - Mean reaction time - Raw score Baseline Difference Day 100 |
| RTI2_v2-baseline | CANTAB RTI - Mean reaction time - Raw score Baseline Difference Day 180 |
| RTIFMRT_1 | CANTAB RTI - Five choice movement time - Raw score at Visit 1 - Baseline |
| RTIFMRT_2 | CANTAB RTI - Five choice movement time - Raw score at Visit 2 – Day 100 |
| RTIFMRT_3 | CANTAB RTI - Five choice movement time - Raw score at Visit 3 – Day 180 |

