9. SPECIFICATIONS OF EFFICACY CRITERIA

Multivariate Efficacy Ensemble

- 1. Processing Speed Index, Changes from Baseline, LPCF, ITT
- 2. Stroop Color-Word Test, Changes from Baseline, LPCF, ITT
- 3. Trail Making Test, Changes from Baseline, LPCF, ITT
- 4. Digit Span, Changes from Baseline, LPCF, ITT
- 5. Montreal Cognitive Assessment, Changes from Baseline, LPCF, ITT
- 6. Stockings of Cambridge (CANTAB), Changes from Baseline, LPCF, ITT
- 7. Reaction Time (CANTAB), Changes from Baseline, LPCF, ITT
- 8 Hamilton Rating Scale for Depression, Changes from Baseline, LPCF, ITT
- 9. Hamilton Anxiety Rating Scale, Changes from Baseline, LPCF, ITT

This ensemble of appropriate single efficacy criteria shall be tested by a multivariate, directional test approach, reflecting the global status of patients in TBI after 3 and 6 months.

All efficacy criteria will be analyze with descriptive group statistics.

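### The listed Symbol Search change variables count correct answers only, so a patient who speeds up by guessing can be scored as improved on a Processing Speed Index component

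*SAP*

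**What the plan says.** The first item of the multivariate ensemble in SAP section 9 is "Processing Speed Index, Changes from Baseline, LPCF, ITT". Protocol 13.4.2 has the same item. Neither document gives a formula for the index.

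The only guide to scoring is the variable list in SAP section 4. For Symbol Search it contains:

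- number correct at the three visits (PSSCNUM_1 to PSSCNUM_3);
- number incorrect at the three visits (PSSINUM_1 to PSSINUM_3), labelled "Symbol Search Number Incorrect at Visit 1 - Baseline", "Symbol Search Number Incorrect at Visit 2 – Day 100" and "Symbol Search Number Incorrect at Visit 3" (Day 180);
- two change variables, PSI_SS_v1-baseline, "Symbol Search Number Correct Baseline Difference Day 100", and PSI_SS_v2-baseline, "Symbol Search Number Correct Baseline Difference Day 180".

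No change variable is listed for the incorrect count, and no score combines the two counts. The other index subscore, Digit Symbol Coding, also has change variables for number correct only, and no error count is listed for it. For the Multitasking Test the same list does carry errors forward, as in "Total Incorrect Baseline Difference Day 100". COMP1 and COMP2 are named as composite scores without a formula.

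Protocol 9.1 says that the index covers, among other skills, "discriminating between and sequentially ordering visual information". It gives no scoring rule.

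**The concern.** A count of correct answers rises with the number of items attempted, even when the added answers are guesses. A wrong answer earns nothing, but it also costs nothing. If a patient moves from careful to hasty responding between baseline and follow-up, the listed change variable can record a gain although the patient discriminates the symbols no better, or worse. Accuracy is part of the construct that the protocol describes, and the counts needed to see the shift are recorded at every visit.

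Two things are at stake. The first is validity: a changed trade-off between speed and accuracy can be read as cognitive benefit on part of a primary item. The second is pre-specification. SAP 12.2 promises a primary analysis fixed in advance, yet the use of a recorded error count is left open, and the two obvious scores can differ in sign for the same patient.

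**Working it through.** The documents state no figure for this point, so there is none to reproduce. They also give no item counts, accuracy levels, response format or standard deviations. The numbers below are therefore assumed. They show what the listed rule can do, not how often it does it.

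**Notation.** C is number correct (PSSCNUM) and I is number incorrect (PSSINUM). The listed change is ΔC. The net change is Δ(C − I).

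**Single-patient example (assumed counts).** Baseline: C = 30, I = 2, net 28. Follow-up: C = 36, I = 12, net 24.

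- Listed change: 36 − 30 = +6.
- Net change: 24 − 28 = −4.

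**Case A: careful work unchanged, with g extra items guessed at success probability q.** Then ΔC = gq, which cannot be negative, and Δ(C − I) = gq − g(1 − q) = g(2q − 1).

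| q | g | ΔC | Δ(C − I) |
|---|---|---|---|
| 0.50 | 5 | +2.5 | 0 |
| 0.50 | 20 | +10 | 0 |
| 0.25 | 5 | +1.25 | −2.5 |
| 0.25 | 20 | +5 | −10 |

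**Case B: the whole test done faster at lower accuracy.** Assume 20 attempts at 95% accuracy at baseline, so C = 19, I = 1 and net is 18. With f times the attempts at accuracy p:

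- ΔC = 20(fp − 0.95)
- Δ(C − I) = 20[f(2p − 1) − 0.90]

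| f | p | ΔC | Δ(C − I) |
|---|---|---|---|
| 1.25 | 0.70 | −1.5 | −8 |
| 1.5 | 0.70 | +2 | −6 |
| 2 | 0.60 | +5 | −10 |
| 2 | 0.50 | +1 | −18 |
| 1.5 | 0.90 | +8 | +6 |

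Number correct rises only if f > 0.95/p: 0.95/0.70 = 1.36 at 70% accuracy and 0.95/0.50 = 1.9 at 50%. The net score falls if f < 0.90/(2p − 1), which is 0.90/0.40 = 2.25 at 70%. So at 70% accuracy the two scores have opposite signs for speed-ups between 1.36 and 2.25 times.

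**Reach into the primary test.** Symbol Search is one of two listed index subscores, and the index is one of nine ensemble items. With equal weights, which the documents do not state, its share is 1/2 × 1/9 = 1/18, or about 6%.

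**The case against.** The strongest reply is that section 4 of the SAP is a data dictionary, not a scoring rule. It opens by saying that the whole set of variables was coded for the primary efficacy analysis, and that set includes PSSINUM. COMP1 and COMP2 have no formula. A reader might infer that errors are discarded altogether; the documents do not support that, because the composite could use them. What stands is narrower: no stated rule uses them, and the only Symbol Search changes listed are of correct answers.

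Four further replies have weight.

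- A wrong answer already earns no credit, and haste does not always pay. The first row of Case B shows number correct falling.
- SAP 12.2 calls for descriptive statistics on all variables, so raw error counts would be summarised and a marked rise should be visible. That helps interpretation but leaves the scored change as it is.
- The Multitasking Test is an imperfect precedent. Its errors are carried as a separate change, not deducted, and it is absent from the nine-item ensemble, although it is among the ten primary endpoints. It shows that error change was thought worth deriving elsewhere; it does not show that a net score is the intended form.
- Protocol 9.1 also describes processing speed simply as how fast cognitive operations are carried out. Marking answers without making the discrimination is not that, but the text does not settle the scoring.

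**Conclusion.** The point holds as a weakness in the definition of one component. If the listed derivation is followed, extra guessed items are credited without penalty, and a patient can be scored as improved while correct minus incorrect is unchanged or lower. In the assumed illustrations where that happens, number correct changes by +1 to +10 while the net score changes by 0 to −18.

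A reader might go further and infer that anyone who guesses is scored as improved, that a known share of patients is misclassified, or that the rule favours the rTMS arm. None of these follows. The first depends on how far speed rises against how far accuracy falls. The second would need distributions of both counts, which the documents do not give. The third would need guessing to differ by arm; in a randomised, sham-controlled, double-blind comparison, a shift common to both arms adds noise and weakens validity without favouring either.

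The effect on the global test is diluted as shown above. It is less diluted where the single criteria are assessed, which is a secondary objective. The point is worth correcting because the remedy uses data already collected and closes a choice that could otherwise be made after the results are seen.

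**What to change.** Before unblinding, amend the SAP to:

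1. define the Symbol Search score as PSSCNUM minus PSSINUM at each visit;
2. derive PSI_SS_v1-baseline and PSI_SS_v2-baseline from that score;
3. state how it combines with Digit Symbol Coding to form the Processing Speed Index ensemble item, and how it enters COMP1 and COMP2;
4. report the changes in number correct and number incorrect descriptively, as the variable list already provides for the Multitasking Test.

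A net score can fall below zero, so the text should also say what the worst possible score is for the imputation in Protocol 13.12.3.

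The score itself costs one line of wording and code, with a few sentences for the rest. No new data are needed. The downside is slight added noise where errors are rare.

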5. STUDY OBJECTIVES

5.1. Primary Objective

To assess the efficacy of the combined rTMS and Cerebrolysin treatment versus CRB alone, upon a battery of neurocognitive outcomes at 3 and 6 months post TBI.

5.1.1. Primary Variable

Cerebrolysin and repetitive Transcranial Magnetic Stimulation (rTMS) in patients with Traumatic Brain Injury

- Processing Speed Index
- Stroop Color-Word Test
- Trail Making Test
- Digit Span
- Montreal Cognitive Assessment
- One Touch Stockings of Cambridge (CANTAB)
- Reaction Time (CANTAB)
- Multitasking Test (CANTAB)
- Hamilton Rating Scale for Depression
- Hamilton Anxiety Rating Scale

5.2. Secondary Objectives

- To assess the single efficacy criteria at three and six months post TBI.
- To test ET and qEEG parameters as biomarkers of cognitive dysfunction.
- To assess the safety of rTMS administrated starting with one month after TBI.
- To check assay sensitivity for the primary objective (rTMS + CRB versus CRB alone) by comparing CRB alone versus PLC.

5.2.1 Secondary Variables

- Eye tracking parameters
- Quantitative EEG parameters
- rTMS adverse events

6. STUDY DESIGN

6.1. Overview

Monocentric, randomized, double-blind, phase II study.

6.2. Sample Size

- Treatment Group CRB + rTMS: N=30
- Treatment Group CRB + sham rTMS: N=30
- Treatment Group placebo + sham rTMS: N=30

Sample size calculations were performed using nonparametric methods with the Nnpar 1.0 software from idv Data Analysis and Study Planning.

6.3. Randomisation

Cerebrolysin and repetitive Transcranial Magnetic Stimulation (rTMS) in patients with Traumatic Brain Injury

This study will be performed under double-blind conditions to keep investigators, other study personnel and patients blinded to treatment allocation. Cerebrolysin is an amber-colored solution; therefore, colored infusion lines will be used for drug administration.

A set of envelopes for each patient enrolled should be distributed to the study nurse preparing the ready-to-use-infusion solution. These nurses are only responsible for the preparation and administration of infusion solutions, and they should not be involved in any further study-related procedures. This person should not be allowed to disclose any information about treatment allocation. A treatment envelope should not be opened until the patient's first ready-to-use-infusion has been prepared.

Sham stimulation will be performed with a sham-coil (MCF-P-B 65, Magventure) which has a mechanical outline and sound level identical to MCF-B65, and also provides the same level of cutaneous discofort and muscle twiching as real stimulation. The rTMS (both sham and real) administration will be provided by two rTMS technicians who will not be involved in any further study-related procedures and will not be allowed to disclose any information about treatment procedure.

Patients meeting in- and exclusion criteria will obtain a random number corresponding to the random list generated in advance by a biometrician selected by the sponsor. Based on the random list sealed, opaque randomization/emergency envelops will be provided as follows:

- To the study centre to break blinding if reasonable suspicion of harm to the patients exists
- To the person assigned to prepare the read-to-use-infusion
- To the person assigned to administrate the rTMS protocol.
- To the study coordinator

On opening, the randomization/emergency envelopes are dated (date, hour) and signed by the person who has opened the envelope. The Investigator should promptly document and explain to the Sponsor any premature unblinding of the Investigational Product(s). The whole study will be unblinded after closure of the database and determination of the analysis populations.

7. STUDY SCHEDULE

Screening and Baseline Visit – within 30 days of onset of TBI (Study Day 30+/- 4 days)

- Neurological and physical exam
- Hematology and blood chemistry
- Demographic data
- Medical history
- Concomitant Medication
- Evaluation Scales

Cerebrolysin and repetitive Transcranial Magnetic Stimulation (rTMS) in patients with Traumatic Brain Injury

Version 1.0

- Processing Speed Index
- Stroop Color-Word Test
- Trail Making Test
- o Digit Span
- Montreal Cognitive Assessment
- Hamilton Anxiety Rating Scale
- Hamilton Rating Scale for Depression
- One Touch Stockings of Cambridge
- o Multitasking Test
- Reaction Time
- ET
- qEEG

Visit 1 – Efficacy Evaluation (study day 101+/- 7days)

- Neurological and physical exam
- Evaluation Scales
 - Processing Speed Index
 - Stroop Color-Word Test
 - o Trail Making Test
 - o Digit Span
 - Montreal Cognitive Assessment
 - o Hamilton Anxiety Rating Scale
 - Hamilton Rating Scale for Depression
 - One Touch Stockings of Cambridge
 - Multitasking Test
 - Reaction Time
- ET
- qEEG

Visit 2 – Efficacy Evaluation (study day 180+/- 4 days)

- Neurological and physical exam
- Evaluation Scales
 - Processing Speed Index
 - Stroop Color-Word Test
 - Trail Making Test
 - o Digit Span
 - Montreal Cognitive Assessment
 - o Hamilton Anxiety Rating Scale
 - Hamilton Rating Scale for Depression
 - One Touch Stockings of Cambridge
 - o Multitasking Test
 - Reaction Time
- ET

Cerebrolysin and repetitive Transcranial Magnetic Version 1.0 Stimulation (rTMS) in patients with Traumatic Brain Injury

• qEEG

Treatment cycles:

- Study days 31-40,
- Study days 61-70
- Study days 91-100

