6. SELECTION AND WITHDRAWAL OF PATIENTS

6.1. Patient Inclusion Criteria

- Traumatic brain injury onset 30 days prior to screening
- CT/MRI– focal and/or diffuse lesions
- Age: 18-70 years, inclusive
- Pre-Trauma Karnofsky Index 100
- Patient is willing and able to comply with the protocol requirements for the duration of the study

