7.1.1. Dosage, Formulations and administration

Cerebrolysin Solution for Injection

IV Cerebrolysin (CRB), 30 ml diluted in 0.9% saline solution up to 250 ml, daily during 10 consecutive working days with 3 treatment cycles during study days 32-40, 61-70 and 91-100).

Repetitive Transcranial Magnetic Stimulation (rTMS)

The rTMS treatment will be performed daily during 10 consecutive working days with 3 treatment cycles during study days 32-40, 61-70 and 91-100).

The medical device MagPro X100 (MagVenture, Denmark) will be used for repetitive stimulation with a figure-8 coil (MCF-B65). The coil will be hold tangential to the scalp with the handle pointing upwards. For localizing the left dorsolateral prefrontal cortex (DLPFC) stimulation, we will use the 10-20 EEG system by placing the coil at F3. The stimulation parameters for DLPFC will be set up at 10 Hz and 1,200 stimuli/day, with an intensity of 120% of resting motor threshold. The resting motor threshold is determined at the beginning of the first treatment session and is defined as the minimal intensity at which at least five of 10 motor evoked potentials are 50 μ V in amplitude in the pollicis abductor brevis. For detailed information (SmPCs) on these products please refer to Appendix 1.

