11. STUDY SCHEDULE

11.1. Procedures at Each Visit

Screening and Baseline Visit – within 30 days of onset of TBI (Study Day 0)

- Neurological and physical exam
- Hematology and blood chemistry
- Demographic data
- Medical history
- Concomittant Medication
- Evaluation Scales
 - Processing Speed Index
 - Stroop Color-Word Test
 - Trail Making Test
 - Digit Span
 - Montreal Cognitive Assessment
 - Hamilton Anxiety Rating Scale
 - Hamilton Rating Scale for Depression
 - One Touch Stockings of Cambridge
 - Multitasking Test
 - Reaction Time
- ET

Date: 040418

STUDY ID: CAPTAIN - rTMS

Scales

Scales

qEEG

Treatment cycles

Each patient shall receive three cycles of treatment of 10 infusions on 10 consecutive days

- Study days 31-40,
- Study days 61-70
- Study days 91-100

Visit 1 – Efficacy Evaluation (study day 101)

- Neurological and Physical exam
- Evaluation
 - Processing Speed Index
 - Stroop Color-Word Test
 - Trail Making Test
 - Digit Span
 - Montreal Cognitive Assessment
 - Hamilton Anxiety Rating Scale
 - Hamilton Rating Scale for Depression
 - One Touch Stockings of Cambridge
 - Multitasking Test (MTT)
 - Reaction Time
- ET
- qEEG

Visit 2 – Efficacy Evaluation (study day 180)

- Neurological and Physical exam
- Evaluation
 - Processing Speed Index

Date: 040418

- Stroop Color-Word TestTrail Making Test
- Digit Span
- Montreal Cognitive Assessment (
- Hamilton Anxiety Rating Scale
- Hamilton Rating Scale for Depression
- One Touch Stockings of Cambridge
- Multitasking Test (MTT)
- Reaction Time
- ET
- qEEG

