13.2. Demographic and Other Baseline Characteristics

Patients' demographics will be obtained at Screening (study day 30), alongside medical history, neurological and physical examinations and hematology and blood chemistry will be obtained.

Females who are pregnant or lactating will be excluded from the study. However, females of child bearing potential taking acceptable contraceptive precautions can be included. A highly effective method of birth control and one which is acceptable for this study, is defined as those which result in a low failure rate (i.e. less than 1% per year) when used consistently and correctly such as implants, injectables, combined oral contraceptives, some IUDs, sexual abstinence or vasectomised partner.

Some concomitant medication will exclude the patient from the study: steroids, Ca2+-channel blockers or major anticoagulants (e.g., warfarin and other coumarin derivates), monoamine oxidase inhibitors, antipsychotic drugs or nootropic molecules. All other concomitant medications and therapies will be recorded in the CRF.

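### The study-day calendar is inconsistent: baseline is Day 0 in the protocol but Day 30±4 in the SAP, no time origin is defined, and the SAP window for Visit 1 overlaps treatment cycle 3

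*SAP*

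**What the plan says.** **Baseline.** Protocol section 11.1 has "Screening and Baseline Visit – within 30 days of onset of TBI (Study Day 0", and the protocol synopsis also uses day 0. SAP section 7 has "Screening and Baseline Visit – within 30 days of onset of TBI (Study Day 30+/- 4 days". SAP section 13.2 repeats the later day ("Patients' demographics will be obtained at Screening (study day 30"), so it is not a slip in one line. Protocol section 6.1 requires "Traumatic brain injury onset 30 days prior to screening".

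**Follow-up visits.** SAP section 7 gives "Visit 1 – Efficacy Evaluation (study day 101+/- 7days" and places Visit 2 at day 180 ± 4. Protocol section 11.1 gives days 101 and 180 without windows.

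**Treatment days.** SAP section 7 lists cycle 1 as "Study days 31-40", with cycles 2 and 3 on days 61 to 70 and 91 to 100. Protocol section 11.1 lists the same days and says "Each patient shall receive three cycles of treatment of 10 infusions on 10 consecutive days". Protocol section 7.1.1 says "daily during 10 consecutive working days with 3 treatment cycles during study days 32-40, 61-70 and 91-100". The synopsis combines working days with days 31 to 40.

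**Not stated.** Neither document defines the origin of the study-day count, says that baseline testing must precede the first session, or says that Visit 1 must follow the last one.

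**The concern.** Every item in the efficacy ensemble is a change from baseline (Protocol section 13.4.2, SAP section 9), and the two follow-up visits are tested together (Protocol section 13.4.1). The baseline date therefore enters every primary value, and Visit 1 supplies half of them.

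If the time origin is unclear, so is the estimate. A change over 101 days that begins with an untreated month is a different quantity from a change over 71 days that begins at about the first session. The objectives are stated as times after injury, so their meaning also depends on what Day 0 is. If Visit 1 may fall inside cycle 3, some patients are assessed after a partial course and others after a full one, under a single label. Two analysts could each follow the documents and disagree on which assessments are valid.

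**Working it through.** The plan gives no figure of its own to reproduce. The check is day-count arithmetic on the scheduled days.

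**1. Windows (nominal day ± tolerance, SAP section 7)**
- Baseline: 30 ± 4 = days 26 to 34 (9 days)
- Visit 1: 101 ± 7 = days 94 to 108 (15 days)
- Visit 2: 180 ± 4 = days 176 to 184 (9 days)

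**2. Overlap with the treatment days**
- Visit 1 and cycle 3 (days 91 to 100): days 94 to 100, which is 7 of 15 permitted days.
- Baseline and cycle 1 (days 31 to 40): days 31 to 34, which is 4 of 9 permitted days; days 32 to 34 are after the first treatment day. With cycle 1 on days 32 to 40, the overlap is days 32 to 34 (3 of 9).
- Visit 2: no overlap.

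**3. Course still outstanding at a day-94 visit**
- Planned sessions: 3 cycles × 10 = 30.
- With daily dosing on calendar days from day 91, 3 sessions (days 91 to 93) are complete before day 94, or 4 if that day's session comes before testing. Remaining: 10 − 4 = 6 to 10 − 3 = 7, or 20% to 23% of 30.
- With working-day dosing the count changes. If day 91 is a Friday, day 94 is the Monday and only one session precedes it, leaving 8 or 9.

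**4. Interval from baseline**
- To Visit 1: protocol 101 − 0 = 101 days; SAP 101 − 30 = 71 days, range 94 − 34 = 60 to 108 − 26 = 82.
- To Visit 2: protocol 180 − 0 = 180 days; SAP 180 − 30 = 150 days, range 176 − 34 = 142 to 184 − 26 = 158.

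**5. Time since injury under each origin**
- Counted from injury: first session day 31, Visit 1 day 101, Visit 2 day 180 (1.0, 3.3 and 5.9 months at 30.44 days per month). This fits the stated one, three and six months.
- Counted from a baseline visit held x days after injury: 31 + x, 101 + x and 180 + x. For x from 0 to 30 this gives 31 to 61, 101 to 131 and 180 to 210 days. If section 6.1 is read literally, x = 30, and the values are 61, 131 and 210 days (2.0, 4.3 and 6.9 months). This does not fit.

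**6. Length of a cycle**
- Days 31 to 40 are 10 days; days 32 to 40 are 9.
- Ten consecutive working days span 12 calendar days from a Monday start and 14 from any other weekday. A cycle starting on day 91 would end on day 102 or 104, after the nominal Visit 1 on day 101.

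**The case against.** **Baseline after treatment start.** A reader might infer from the days 26 to 34 window that baseline can be measured after treatment has begun. The documents do not support this as a planned order. Screening and baseline are one visit, and a random number is issued only once eligibility is met (Protocol section 6.4, SAP section 6.3), so treatment should follow that visit. The same SAP line also limits baseline to 30 days after onset. If days count from injury, the +4 days contradict that limit. The baseline overlap is therefore an inconsistent tolerance. This part of the objection stands.

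**One natural time origin.** The objectives, the inclusion criterion and the SAP screening day all fit counting from injury, so the protocol's Day 0 may be only a labelling error. That is plausible, but neither document says so, and the label appears in both the synopsis and section 11.1.

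**No bias between arms.** A reader might also infer a biased comparison. The trial is randomised and double-blind, and all arms share one calendar and one set of windows, so mistiming should be similar across arms. Extra untreated recovery would occur in every arm. This stands too: dilution and ambiguity are the likely effects.

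**Partial safeguards.** SAP section 4 lists visit dates and variables whose names suggest date deviations for the two follow-up visits. Protocol section 11.2 records the date and time of each administration, and section 13.13.1 provides a blind review of violations. These make a check possible, but the deviation variables are undefined, there is none for baseline, and no rule says how they are used.

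None of these points removes the Visit 1 overlap.

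**Conclusion.** The calendar conflict is real, and the Visit 1 overlap is its firmest part: 7 of 15 permitted days lie within cycle 3 and nothing in either document prevents a visit on them. That is a count of permitted days, not an expected share of patients. The figure of 6 to 7 of 30 sessions outstanding is a day-94 extreme that assumes daily calendar dosing.

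The two baseline labels shift the nominal follow-up intervals by 30 days (101 against 71; 180 against 150). The spread of up to 30 days in time since injury arises only if Day 0 is the baseline visit and patients are screened anywhere from 0 to 30 days after injury.

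The baseline window needs correcting, but on-treatment baselines are unlikely. Visit 2 is unaffected by overlap. The documents give no basis for a claim of between-arm bias, and the loss of effect from mistimed Visit 1 values cannot be sized from them, because they do not say how often such visits would occur.

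**What to change.** 1. Define one Day 0, identically in both documents, and correct the baseline day to match. The objectives, being stated as times after injury, fit a count from injury.
2. Have the clinical team reconcile the treatment-day passages: days 31 to 40 against 32 to 40, and working against consecutive days. This review takes no position on which is right.
3. Once that is settled, set the assessment windows so that baseline closes before the first session and Visit 1 opens after the scheduled end of cycle 3.
4. Keep all observed values in the ITT analysis. Discarding Visit 1 results there because of session timing would remove outcomes on a post-randomisation basis, and the missing-data codes in SAP section 12.1 have no category for a valid but excluded test.
5. Add a sensitivity or per-protocol analysis that excludes baselines taken after the first session and Visit 1 values taken before the last session actually received. Wording it by sessions received keeps the rule defined for patients who stop early.

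The cost is a clarification in each document and a date check. Visit dates are already in the SAP variable list and administration dates are already recorded in the CRF, so no new data are needed.
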